6.2. Trial Period

D1 of Cycle 1 [Vital signs] [Physical examinations and weight measurement] [Intravenous drip of SHR-1210] [Dispensation of apatinib] [Administration of apatinib]

Within 24 h after the first dose of SHR-1210, the subjects should be closely monitored for acute allergic reactions. If an acute allergic reaction occurs, it should be treated according to the medical practice of the hospital and relevant guidelines.

In order to improve the compliance of the subjects and ensure that apatinib is taken after breakfast every day, only SHR-1210 is administered on D1 of Cycle 1 while the oral administration of apatinib is started on D2 after breakfast, and will be continuously given in cycles of 4 weeks.

D15 of Cycle 1 [Hematology] [Blood biochemistry] [Urinalysis] [Stool routine] [Coagulation function] [Vital signs] [Physical examination and weight measurement] [ECG] [Intravenous drip of SHR-1210] [Adverse events] [Concomitant medication]

D1 of subsequent cycles [Routine blood test] [Biochemistry] [Routine urinalysis] [Routine stool test] [Coagulation] [Vital signs] [Physical examinations and weight measurement] [ECOG PS] [ECG] [SHR-1210 IV drip infusion] [Adverse events] [Concomitant medication]
[Retrieval/dispensing of apatinib]

D15 of subsequent cycles: [Hematology] [Blood biochemistry] [Urinalysis] [Vital signs] [Physical examination and weight measurement] [Intravenous drip of SHR-1210] [Adverse events] [Concomitant medication]

A window period of ± 3 d is set and the intravenous administration of SHR-1210 should be carried out after the evaluation of examinations and tests specified in the flowchart is completed.

[Imaging evaluation] During the treatment period, the imaging examination should be performed under the same conditions as those of the baseline examination (layer thickness of the scan, use of contrast agent, etc.), and the baseline lesions should be checked every 2 cycles during the first 12 treatment cycles (bone scan will be performed if bone progression is suspected or CR is confirmed), and then once every 3 cycles thereafter. Appropriate examination may also be performed if new lesions are suspected. The first documentation of PR/CR in a subject must be verified 4 weeks \pm 7 days later. A radiological confirmation is required 4-6 weeks after the first documentation of disease progression as per RECIST 1.1 (except those with rapid progression or significant clinical progression);

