7. EVALUATIONS

7.1. Efficacy Evaluation

7.1.1. Efficacy indicators

The primary efficacy endpoint for this study is the objective response rate (ORR) as assessed by independent review committee (IRC) as per RECIST 1.1.

Objective response rate (ORR): The proportion of subjects with a best overall response (BOR) of complete response (CR) or partial response (PR) as per RECIST 1.1 criteria.

CR and PR must be verified at least 4 weeks \pm 7 days after their first presence.

Best overall response refers to the best response assessed by the IRC, or the best response from the date of first dose to the first documentation of progression as per RECIST 1.1 or to the start of a new anti-tumor treatment (whichever comes first).

For subjects without documented progression or new anti-tumor treatment, the best overall response will be determined on the basis of all efficacy assessments.

For subjects who continue SHR-1210 treatment beyond progression, the best overall response should be based on the efficacy assessment at the time of first documented progression as per RECIST 1.1.

Secondary efficacy endpoints include:

- Objective response rate as assessed by the investigator as per RECIST 1.1;
- Progression-free survival (PFS): The period of time from the date of first dose to the date of the first recorded tumor progression (according to RECIST v1.1 criteria, regardless of whether treatment is continued) or death of any cause (whichever comes first).

When determining PFS, clinical exacerbations without definite evidence of disease progression (as per RECIST 1.1) is not considered progression. For subjects who die without any prior reports of progression, the date of death is considered the date of progression. Subjects without disease progression or death will be censored on the date of their last evaluable tumor assessment. Subjects without tumor assessments during the study or death will be censored on their date of first dose. Subjects who discontinue the treatment for reasons other than disease progression (no subsequent tumor assessments) will be censored on the date of their last evaluable tumor assessment. Subjects without disease progression before starting a new anti-tumor therapy will be censored on the date of their last evaluable tumor assessment prior to the start of new anti-tumor therapy.

- Time to objective response (TTR) is defined as the period of time from the date of first dose to the first documented tumor response (as per RECIST 1.1).

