**4.1.2.6. Progression-free survival (PFS)**

Progression-free survival (PFS): It is defined as the time from the date of first administration to the date of first recorded tumor progression (assessed as per RECIST v1.1 or mRECIST) or the date of death due to any cause, whichever occurs first.

Censoring rules:

- If there is no baseline tumor measurement or there is baseline tumor evaluation but with missing tumor evaluation after baseline, censoring will be based on the date of first administration.
- If the subject does not have PD or die prior to the termination of the study/cut-off date for analyses or dropout and is not using a new anti-cancer drug prior to PD or death, censoring will be based on the date of the last valid efficacy evaluation.
- If a new anti-cancer treatment has been initiated before PD or death, censoring will be based on the date of the last valid efficacy evaluation prior to the new anti-cancer treatment.

- For death or progression with the absence of two or more planned visits (two visits are planned to be conducted at 26 weeks after 12 cycles of first administration and at 18 weeks prior to 12 cycles), censoring will be based on the date of the last valid efficacy evaluation prior to death or progression.
- For death or PD with the absence of two planned visits after first administration, censoring will be based on the date of first administration.

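### Read literally, the SAP's first PFS censoring rule censors at first dose a subject who dies with no post-baseline scan, contrary to the SAP's own PFS definition and to the protocol

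*SAP*

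**What the plan says.** **SAP 4.1.2.6 (PFS).** The event is first recorded progression or "the date of death due to any cause, whichever occurs first". Five censoring rules follow.

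- Rule 1 covers subjects with no baseline tumor measurement, and those for whom "there is baseline tumor evaluation but with missing tumor evaluation after baseline, censoring will be based on the date of first administration". Death is not mentioned.
- Rule 2 opens "If the subject does not have PD or die prior to the termination of the study/cut-off date for analyses or dropout", so it is confined to subjects who have neither progressed nor died.
- Rule 3 censors at the last valid evaluation before a new anti-cancer treatment that begins before progression or death.
- Rule 4 censors a death or progression that follows two or more missed visits at the last valid evaluation before it.
- Rule 5 reads "For death or PD with the absence of two planned visits after first administration, censoring will be based on the date of first administration".

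**Protocol 7.1.1.** "For subjects who die without any prior reports of progression, the date of death is considered the date of progression". It continues: "Subjects without tumor assessments during the study or death will be censored on their date of first dose". Taken with the sentence before it, this second rule can only mean subjects who have neither an assessment nor a death. The protocol's PFS definition has no missed-visit rule.

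**Context.** SAP 5.4 analyses PFS on the full analysis set, which requires a dose but no scan (SAP 5.1.1.1). SAP 5.4.2.2 uses Kaplan-Meier for the median and the 6-, 9- and 12-month rates. SAP sections 1 and 2 state that the plan is drafted from protocol version 3.0, and the SAP declares no departure from it on PFS.

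**The concern.** A subject who dies early and was never scanned after baseline meets the SAP's event definition and also the literal terms of rule 1. Nothing says which takes precedence. A programmer who applies rule 1 as written will censor the death on Day 1. One who follows the protocol will count it as an event on the date of death. The same data then give two different PFS curves.

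The error would run in one direction. These are among the shortest PFS times in the trial, and censoring them because no scan was done is informative, since death is what prevented the scan. The trial has one arm, so no control arm shares the bias, and the SAP plans no PFS sensitivity analysis that would count these deaths.

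**Working it through.** **1. When the first scan is due.** Protocol 6.2: "the baseline lesions should be checked every 2 cycles during the first 12 treatment cycles". A cycle is 4 weeks, so 2 × 4 = week 8, with a window of ±7 days (weeks 7 to 9). The design summaries in protocol 3.1 and SAP 2.1 give the interval in weeks rather than cycles. However, the SAP's own missed-visit limits reproduce only from the cycle-based schedule: 2 × 8 + 2 = 18 weeks in the first 12 cycles, and 2 × 12 + 2 = 26 weeks afterwards. Week 8 is therefore used here.

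**2. What rule 1 does to such a death.** SAP 5.4.2.2 computes PFS as (event or censoring date − first dose date + 1)/30.4375. Censored at first dose, the subject contributes (0 + 1)/30.4375 = 0.03 months. The subject leaves the risk set before any event can occur and adds nothing to the curve.

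**3. Formula.** Let q be the fraction of the full analysis set that dies unscanned before the first scan, and let S(t) be PFS in everyone else. Rule 1 read literally reports S(t). The protocol definition gives (1 − q)S(t) once those deaths have occurred. With exponential S(t) and median m, the protocol median is m × log2[2(1 − q)], against m under rule 1.

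**4. Illustration.** The documents give neither q nor a PFS median; both are assumptions. The nearest figures are the median times to progression of 3.32 and 4.21 months on apatinib alone (protocol 1.1), so m = 4.

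| q | Subjects of 120 | Median, months (rule 1: 4.00) | 6-month PFS (rule 1: 35.4%) |
|---|---|---|---|
| 3% | about 4 | 4 × log2(1.94) = 3.82 | 0.97 × 35.4% = 34.3% |
| 5% | 6 | 4 × log2(1.90) = 3.70 | 0.95 × 35.4% = 33.6% |
| 10% | 12 | 4 × log2(1.80) = 3.39 | 0.90 × 35.4% = 31.8% |

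The gap in months grows with the median. At m = 5.5 and q = 10%, the median falls from 5.50 to 4.66 months and 6-month PFS from 46.9% to 42.3%.

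**5. Is the range of q reasonable?** Protocol 1.1 cites 12-month survival on nivolumab of 58–60% after sorafenib and 73% without it. With constant hazard, the proportion dead by day 56 is 1 − 0.58^(56/365.25) = 8.0%, 1 − 0.60^(56/365.25) = 7.5%, and 1 − 0.73^(56/365.25) = 4.7%. Eligibility (ECOG 0–1, Child-Pugh A, expected survival of at least 12 weeks) should lower these figures, and any death preceded by a scan drops out of q. So 10% is a high value.

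**6. Against sampling error.** For 120 uncensored exponential times with m = 4, the standard error of the median is about 4/(ln 2 × √120) = 0.53 months. The shifts at q = 3% and 5% are 0.18 and 0.30 months, both below one standard error. At 10% the shift is 0.61 months. In simulated trials of 120 subjects scanned every 8 weeks, the Kaplan-Meier median was identical under both rules in roughly 86–89%, 78–81% and 56–58% of trials for q = 3%, 5% and 10%, because progression dates fall on the scan grid. The landmark rates still shift by the factor (1 − q).

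**The case against.** **The authors may not have meant it.** The SAP's definition makes any death an event. Rule 5 would be largely redundant for deaths if rule 1 already took every unscanned death, which suggests that an early death before two missed visits was intended to count. Rule 1 also appears in nearly the same words under TTP, where it is correct because death is not a TTP event. It appears again under DOR, where it has no effect because every responder has a post-baseline scan. It may simply have been carried over. This stands: intent is unclear, and it would be wrong to say that the SAP deliberately removes early deaths. But no rule says that they are events, so the text still needs correcting.

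**Not every early death is affected.** A reader might infer that all deaths before week 8 are censored on Day 1. The documents do not support that. Protocol 6.2 allows unscheduled imaging when progression is suspected, and 6.3 calls for imaging at the end of treatment or withdrawal if none was done in the previous 4 weeks. Rule 1 reaches only deaths with no post-baseline evaluation. Its other branch, no baseline measurement, should be nearly empty because a measurable lesion is required for entry.

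**The stakes are limited.** PFS is secondary and has no decision rule; the success criteria in SAP section 3 use ORR alone. An unscanned early death counts as a non-responder in the full-analysis-set ORR and as an event in OS. SAP 5.4.2.2 tabulates censoring by reason, so Day-1 censoring would be visible. All of this stands and lowers the priority. A table of censoring reasons does not correct the curve, however.

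**Conclusion.** The conflict is real on the text. SAP rule 1, read literally, censors at first dose deaths that both the SAP's PFS definition and protocol 7.1.1 treat as events. The direction of the bias is certain: it can only raise PFS. The size cannot be obtained from the documents. The illustrative reductions, from 4.00 to 3.82, 3.70 or 3.39 months, rest on an assumed early-death fraction, an assumed median and exponential PFS. Only fractions near 10% move the median by more than one standard error.

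Correcting rule 1 alone would not bring the two documents into line. Rules 4 and 5 name death explicitly and censor it after missed visits, whereas the protocol counts it. Even if rule 1 was meant to exclude deaths, rule 5 still conflicts with the protocol.

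A reader might infer that the trial's efficacy conclusion is compromised. It is not: ORR and OS are unaffected. This should be fixed before the PFS analysis, and it is no threat to the primary result.

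**What to change.** 1. Limit PFS rule 1 to subjects with no baseline or no post-baseline tumor evaluation **and** no death. State that a death with no post-baseline evaluation is a PFS event on the date of death.
2. Reconcile rules 4 and 5 with protocol 7.1.1. Either make the protocol definition the main PFS analysis and keep the missed-visit censoring of deaths as a labelled sensitivity analysis, or declare and justify the departure from the protocol.
3. Leave the TTP rules as they are.

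The cost is one sentence and one programming condition for rule 1, plus a short statement and, if that option is chosen, one additional PFS run for rules 4 and 5. Reported PFS will be slightly less favourable if any such deaths occur.

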Apatinib administration ^[20]			Oral administration once a day after meal						
Apatinib dispensing/retrieval ^[21]			×		×		×		
Imaging Evaluation									
Imaging examination ^[22]	×		Once every 2 cycles in the first 12 cycles of dosing, followed by once every 3 cycles				×		
Follow-Ups After Discontinuation									
Time to progression ^[23]							Imaging evaluations are performed once every 3 months (± 7 d) until disease progression or start of new anti-tumor treatments (for subjects with non-radiological PD)		
Death ^[24]									×
Blood Sampling and Tumor Tissue Sampling									
Blood/tissue sampling for biomarkers ^[26]	×								

Notes:

- [1] Tumor history/past medical history: tumor diagnosis, surgical history, interventional therapy, local ablation therapy, systemic treatment, radiation therapy, as well as past treatments of other conditions, history of cancers other than HCC.
- [2] Concomitant medications and treatments received within 30 days prior to the first dose and during the study period should be recorded. Once a subject discontinues the investigational treatment, only concomitant medication or treatment for new or unresolved treatment-related adverse events are recorded, until 30 days after the last dose.
- [3] Routine blood test: WBC, neutrophils, lymphocytes, RBC, hemoglobin, and platelets. Performed within 7 days prior to enrollment, on Day 15 of Cycle 1, Day 1 and 15 of subsequent cycles, at the end of study, and 30 days after the end of treatment.
- [4] Blood biochemistry: total bilirubin, direct bilirubin, ALT, AST, AKP, γ -GT, total protein, albumin, urea/blood urea nitrogen, creatinine, uric acid, fasting blood glucose, TG, cholesterol, potassium, sodium, chlorine, calcium, phosphorus, blood lipase (only during the screening period and in case of subsequent abdominal pain, abdominal distension and other symptoms of suspected pancreatitis), blood amylase (only during the screening period and subsequent abdominal pain, abdominal distension and other symptoms of suspected pancreatitis). It is carried out within 7 days before enrollment, on Day 15 of Cycle 1, Day 1 and Day 15 of subsequent cycles, at the end of study, and 30 days after the treatment.

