- During the treatment period, the imaging examination should be performed under the same conditions as those of the baseline examination (layer thickness of the scan, use of contrast agent, etc.), and the baseline lesions should be checked every 2 cycles during the first 12 treatment cycles (bone scan will be performed if bone progression is suspected or CR is confirmed), and then once every 3 cycles thereafter. Appropriate examination may also be performed if new lesions are suspected. The first documentation of PR/CR in a subject must be verified 4 weeks \pm 7 days later. A confirmation is required 4-6 weeks after the first documentation of disease progression as per RECIST 1.1 (except those with rapid progression or significant clinical progression);
- The window period for imaging examination schedule is \pm 7 days. Unscheduled imaging examinations can be performed when progressive disease is suspected (such as worsening of symptoms).
- [23] In addition to the progressive disease as evidenced by imaging, subjects who have ended the trial treatment for other reasons must be evaluated at the end of treatment if the imaging examination is not performed within 4 weeks prior to the end of the trial. At the same time, tumor efficacy is followed up every 3 months after the end of the trial until records confirm the progressive disease or initiation of new tumor treatments.
- [24] Survival follow-up: After the trial treatment is discontinued, the survival status and subsequent anti-cancer treatment can be collected through clinical or telephone follow-ups every 1 month until death.
- [25] 10 mL of blood, and paraffin-embedded tumor tissue specimens or fresh biopsy samples (size of a soybean) are collected. At least 10 slides are required, including 3-5 slides of 3-5 μ m thickness for PD-L1, SOAT1, NPC1, and TGF- β testing, and 5-8 paraffin sections (paraffin blocks may be collected directly, without mounting onto slides) of 8-10 μ m thickness, otherwise fresh biopsy samples (pea-size) are required for testing biomarkers such as tumor mutational burden (TMB). See the laboratory manual for blood and tumor tissue sampling/sample collection, and disposal.

Abbreviations

Abbreviations and Terms	Full Name
ADA	Anti-drug antibody
ADRs	Adverse drug reactions
AE	Adverse event
AFP	A-fetoprotein
AKP	Alkaline phosphatase
ALT	Alanine aminotransferase
ANC	Absolute neutrophil count
APTT	Activated partial thromboplastin time
ASCO	American Society of Clinical Oncology

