6.3. End of Treatment/Withdrawal

The treatment shall be discontinued if events specified in "Section 4.3.1. Criteria for Discontinuation" occur. At the end of the study treatment or upon withdrawal from the study (a window period of ± 3 d), if a subject has not undergone examinations within 14 days prior to the end of the study, the subject should undergo the following examinations:

[Hematology] [Blood biochemistry] [Urinalysis] [Stool routine] [Coagulation function]
[Pregnancy test] [Thyroid function test] [Alpha-fetoprotein] [HBV DNA and HBsAg quantitative tests] [Myocardial zymogram] [Vital signs] [Physical examination] [ECOG PS] [ECG]
[Echocardiography] [Blood pressure monitoring] [Adverse events] [Concomitant medication]
[Return of apatinib]

If a subject has not undergone imaging examinations within 4 weeks prior to the end of the study, the subject should undergo an imaging examination for response assessment at the end of the study treatment or upon withdrawal from the study (a window period of ± 3 d). For subjects with PD demonstrated by non-imaging evidence (intolerability, other conditions), a tumor evaluation is carried out every 3 months until PD, death, or the initiation of other anti-tumor treatments.

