7.1.2. Efficacy evaluation

To evaluate the primary and secondary efficacy endpoints of SHR-1210 in combination with apatinib mesylate in patients with advanced hepatocellular carcinoma as per RECIST v1.1 (Appendix II).

Baseline lesions will be assessed once every 2 cycles during the first 12 treatment cycles (bone scan will be performed if bone progression is suspected or CR is confirmed) and then once every 3 cycles thereafter. Tumor assessments are not affected by treatment discontinuation or delay. Tumor assessments may also be performed if new lesions are suspected. The first PR/CR must be confirmed after 4 weeks \pm 7 days. As per RECIST 1.1, imaging confirmation is required 4-6 weeks after the first documentation of disease progression (except those with rapid progression or significant clinical progression).

For the record and assessment of survival, the subjects will be followed up by telephone for survival once every month after leaving the group until death, lost to follow-up, withdrawal of informed consent, or termination of the study by Hengrui.

Assessments of tumor response include all known or suspected lesions.

Radiographic examination includes CT or MRI scans of the chest, abdomen, or pelvis. Brain CT or MRI is performed for subjects with known or suspected brain metastasis, while bone scan is performed for subjects with known or suspected bone metastasis (**See 7.1 Imaging Examinations for details**).

If discontinuation is indicated by deterioration of overall health in absence of objective evidence of disease progression, such event shall be reported as symptomatic deterioration.

If a subject has not undergone imaging examinations within 4 weeks prior to the end of the study, the subject should undergo an imaging examination for response assessment at the end of the study treatment or upon withdrawal from the study. For subjects with PD demonstrated by non-imaging evidence (intolerability, other conditions), a tumor evaluation is carried out every 3 months until PD, death, or the initiation of other anti-tumor treatments.

Secondary efficacy endpoints in this study include ORR, PFS, DOR, and DCR assessed by the Independent Review Committee (IRC) in accordance with the mRECIST criteria.⁷

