#### **4.1.2.4. Time to progression (TTP)**

Time to progression (TTP): It is defined as the time from the date of first administration to the date of first occurrence of imaging PD (assessed by IRC or investigators as per RECIST v1.1 or mRECIST).

Censoring rules:

- If there is no baseline tumor measurement or there is baseline tumor measurement with absence of post-baseline tumor evaluation, censoring will be based on the date of first administration.
- If the subject does not have PD prior to the termination of the study/cut-off date for analyses or dropout and is not using a new anti-cancer drug prior to PD, censoring will be based on the date of the last valid efficacy evaluation.
- If a new anti-cancer treatment has been initiated before PD, censoring will be based on the date of the last valid efficacy evaluation prior to the new anti-cancer treatment.
- If death occurs before PD, censoring will be based on the date of the last valid efficacy evaluation prior to death.
- For PD after the absence of two or more planned visits (two visits are planned to be conducted at 26 weeks after 12 cycles of first administration and at 18 weeks prior to 12 cycles), censoring will be based on the date of the last valid efficacy evaluation prior to PD.
- For PD after the absence of two planned visits after first administration, censoring will be based on the date of first administration.

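### The SAP's 18- and 26-week missed-visit limits fit only on-treatment scans; in the protocol's 3-monthly off-treatment follow-up they contradict the rule's own two-visit wording

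*SAP*

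**What the plan says.** SAP 4.1.2.6 (PFS) and 4.1.2.5 (DOR) set a missed-visit rule that begins "For death or progression with the absence of two or more planned visits". SAP 4.1.2.4 (TTP) has the same rule for progression only: "For PD after the absence of two or more planned visits". When it applies, the event is replaced by censoring at the last valid evaluation before it. All three sections carry the same parenthesis: "two visits are planned to be conducted at 26 weeks after 12 cycles of first administration and at 18 weeks prior to 12 cycles".

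On treatment, the protocol (6.2 and 7.1.2) schedules scans every 2 cycles for the first 12 cycles and every 3 cycles after that, with a ±7-day window. A cycle is 4 weeks.

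Off treatment the schedule is different. The schedule of procedures says: "Imaging evaluations are performed once every 3 months (± 7 d) until disease progression or start of new anti-tumor treatments". Its note 23 says that "tumor efficacy is followed up every 3 months after the end of the trial until records confirm the progressive disease". Protocol 6.3 says that "a tumor evaluation is carried out every 3 months until PD, death, or the initiation of other anti-tumor treatments". An end-of-treatment scan is required only in the case that begins "If a subject has not undergone imaging examinations within 4 weeks prior to the end of the study".

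SAP 2.1 keeps patients who stop for reasons other than progression or death in progression follow-up. It gives no off-treatment scan interval and no separate limit. The protocol's own PFS definition (7.1.1) has no missed-visit censoring, so it cannot settle how the SAP rule should be read.

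**The concern.** The rule is stated twice, once as a count of visits and once in weeks. The two statements agree on treatment but not for patients in 3-monthly follow-up. There, a single missed scan already gives a gap longer than the 18-week figure and close to or above the 26-week figure. By the count such a patient keeps a progression event; by the weeks the event becomes a censored observation at the previous scan. An on-treatment patient who misses one scan keeps the event either way.

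Two programmers working from the same SAP could therefore report different event counts for PFS, TTP and DOR. The affected patients are those who leave treatment without radiological progression and without new therapy.

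**Working it through.** **Inputs.** Cycle 4 weeks (protocol 5.2). Scans every 2 cycles, then every 3 (7.1.2). Window ±7 days (6.2). Off-treatment scans every 3 months ±7 days (schedule of procedures). Limits of 18 and 26 weeks, switching at 12 cycles = 48 weeks from first dose (SAP 4.1.2.4 to 4.1.2.6).

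**Step 1: reproduce the SAP's figures.** The SAP gives no formula. Two scan intervals plus one week at each end gives:
- up to 12 cycles: 8 + 8 + 2 = 18 weeks
- after 12 cycles: 12 + 12 + 2 = 26 weeks

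Both match exactly, so this is the natural, though inferred, origin.

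**Step 2: one missed scan on treatment.** The gap is 16 weeks (14 to 18) before cycle 12 and 24 weeks (22 to 26) after it. Neither exceeds its limit, so words and weeks agree.

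**Step 3: one missed scan off treatment.** Take 3 months as 3 × 30.4375 = 91.3 days = 13.04 weeks.
- Between follow-up scans: 2 × 13.04 = 26.1 weeks, range 24.1 to 28.1.
- From a last on-treatment scan 0 to 28 days before stopping to the second follow-up scan: (182.6 − 7)/7 = 25.1 to (28 + 182.6 + 7)/7 = 31.1 weeks.

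Reading 3 months as anything from 84 to 92 days widens the first range to 22.0 to 28.3 weeks. Every value is above 18.

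**Step 4: share above 26 weeks,** taking scan dates as uniform within their windows and 3 months as 91.3 days. Between follow-up scans it is about 54%. From the last on-treatment scan, placed uniformly over the 28 days before stopping, it is about 95%. If 3 months means exactly 12 weeks, the follow-up gap is 22 to 26 weeks and does not exceed that limit.

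**Step 5: number of PFS events.** The documents give none of the rates needed, so these are assumptions:
- 10 to 20% of 176 patients (120 + 56) stop before cycle 12 without progression or new therapy, at times uniform over weeks 8 to 48.
- 70% of them later progress, with an exponential time from stopping (median 9 months).
- 10 to 20% of scans are missed independently.

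The limit switches from 18 to 26 weeks at week 48. The SAP does not say whether the event date or the last scan selects it, so both were simulated (400,000 patients each). The share is the proportion of progressions with exactly one missed scan and a gap above the limit.

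| Stopping and miss rates | Limit selected by | Share censored | PFS events |
|---|---|---|---|
| 10%, 10% | event date | 9.6% | 176 × 0.10 × 0.7 × 0.096 = 1.2 |
| 10%, 10% | last scan | 10.7% | 176 × 0.10 × 0.7 × 0.107 = 1.3 |
| 20%, 20% | event date | 16.0% | 176 × 0.20 × 0.7 × 0.160 = 3.9 |
| 20%, 20% | last scan | 17.6% | 176 × 0.20 × 0.7 × 0.176 = 4.3 |

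If the event date selects the limit, only about 0.15 to 0.5 of these events fall under the 18-week figure. The rest fall under the 26-week one.

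**The case against.** The strongest reply is that the operative words count visits. One missed off-treatment scan is one visit, so nothing is censored, and the parenthesis never says that a gap above 18 weeks triggers censoring. This stands in part: a reader might infer that the SAP definitely censors after one missed 3-monthly scan, and the text does not support that. What remains is that the SAP prints week figures that give a different answer and does not say which governs.

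A second reply cites protocol 7.1.2: "Tumor assessments are not affected by treatment discontinuation or delay". Read alone, that could mean 8-weekly scans continue after stopping. But the same section goes on to set 3-monthly scans, as do 6.3, the schedule of procedures and its note 23.

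A third reply is that the week limit treats similar uncertainty alike. An on-treatment patient who misses two 8-weekly scans has a 24-week gap and is censored, so censoring a gap of about 26 weeks is defensible. That is a fair argument for a time-based rule, but the SAP does not make it, and its wording counts visits.

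Some cases escape the conflict. Patients who start new therapy are censored anyway. Either drug may continue alone after the other stops for toxicity, so fewer patients leave treatment. Unscheduled imaging can shorten gaps. A death 13 to 18 weeks after the last scan, with one scan missed, is within the 18-week limit.

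**Conclusion.** The inconsistency is real and minor. For patients in 3-monthly follow-up, the week figures and the visit count give different results after one missed scan: always under the 18-week limit, often under the 26-week limit. About 1 to 4 PFS events are affected, on assumed rates for stopping, progression, missed scans and stopping times. TTP and DOR carry the same rule; their counts were not estimated.

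Three stronger readings should be resisted:
- Patients who stop for confirmed CR or after 2 years of SHR-1210 might seem exposed to the 18-week limit. Protocol 4.3.1 allows the CR stop only after 12 cycles, and the 2-year stop is later still. Their follow-up gaps meet the 26-week limit, where one missed scan is borderline.
- The PFS or DOR medians might be thought materially too long. No shift has been computed, and earlier censoring also shrinks the risk set, which acts the other way over part of the curve.
- The primary result might seem in doubt. ORR, its decision rule and the sample size do not use this censoring rule.

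**What to change.** In SAP 4.1.2.4, 4.1.2.5 and 4.1.2.6, define the trigger as two or more consecutive planned scans missed under the schedule in force for that patient: 8-weekly, 12-weekly or 3-monthly. Drop the week figures, or state that they apply only to on-treatment scans. Report the 18/26-week version as a sensitivity analysis, and state there whether the event date or the last scan selects the limit.

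The cost is one reworded rule in three sections, programmed from first-dose, treatment-end and scan dates already collected. No scans or patients are added. The downside is that the few progression dates kept after one missed 3-monthly scan are uncertain by up to about 7 months (31.1 weeks × 7 / 30.4375 = 7.2). The sensitivity analysis would show how much that matters.
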